 The anticipated initial users of the service (including up to 500 "known positives") are recruited (2,500 persons) prior to the HTKs becoming available, and invited to attend a community testing centre on specific day(s). At the centres, metadata will be collected on all individuals (in the form of an electronic questionnaire) and a venous blood sample taken.

In a small number (n ~ 100) of individuals, a capillary blood sample and dried blood spot (DBS) will be taken. This will allow assay optimisation for enzyme immunoassays which may in future use capillary blood samples.

The blood samples will be tested with one or more commercial EIAs. These include products by EuroImmun (anti-Spike) Roche (anti-N) Abbott (anti-N).

Emerging data indicates that anti-N assays have very good performance, with enhanced sensitivity relative to anti-S assays. For all the assays, sensitivity, particularly early in disease and in cases of asymptomatic infection, is less well characterised.

We will use a single assay with the highest published performance available, which we will refer to as the High Performance Assay (HPA). We envisage this will be one of the two available anti-N EIAs. Subject to availability, we will perform both an anti-S and anti-N assay on all samples as well, but the initial analysis of the HTK will be against the HPA. Other experimental assays under development by the DHSC project or PHE may also be used. A plasma bank will be set up, ready to be tested with the HTK in the laboratory once available. The clinical performance of the HTK will be estimated in two separate analyses (1) assuming the HPA is 100% sensitive and specific (which may, however, be incorrect); and (2) Bayesian evidence synthesis methods incorporating other data sources (see below). (Objective 1, 6, 7).

The capillary blood samples will be used to compare EIA signals between samples derived from DBS, venous plasma and capillary plasma samples as part of a proof-of-concept, methods development approach. The 100 sample size is based on the need for at least 10 positives, and is based on an assumed 10% seroprevalence. We will modify the number of capillary samples taken to ensure sufficient positive samples are available based on seroprevalence data.

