- 12. The lithium heparin anticoagulated sample is sent to Oxford Immunotec Ltd, Milton Park, Oxford for T-SPOT SARS-CoV-2 testing. This is a Research Use only (RUO) ELISPOT based kit produced by Oxford Immunotec which is due to be launched on 15 May 2020. It measures the number of CD4 and CD8 cells specifically producing interferon-γ in response to a proprietary mixture of proteins and/or peptides derived from SARS-CoV-2 proteins. The tube sent to Oxford Immunotec will be identified by a study number only. Oxford Immunotec return the results to PHE.
- 13. Banked plasma is analysed for anti-SARS-CoV-2 antibodies using the HPA EIA assay, and other assays as they are developed. Additional samples (capillary blood and/or dried blood spot) will also be banked and despatched to laboratories as directed by the DHSC program evaluating team.
- 14. Banked plasma is made available for laboratory evaluation of HTKs in a laboratory setting, when such kits become available.
- 15. If the subject has requested the result of their serological results, we will provide them when
 - The assays used have been deployed, or are scheduled for deployment, by the NHS at the time of reporting, and so are considered to have a sufficient level of validation.
 - We have sufficient confidence in the technical processes.

Substantial uncertainty remains about the clinical interpretation of these tests (for example – are the individuals protected if seropositive), and data is accruing all the time. The NHS is currently drawing up interpretation guidelines. We will provide the results with an explanation congruent with those issued by the NHS when these complete. We will test these materials with the HRA's Patient and

Evaluating Detection of SARS-CoV-2 antibodies using home test kits (EDSAB-HOME study)

Protocol 30.05.2020 Version 04.03

Public Involvement group before we use them, and provide a report on this activity to the PHE REC before going ahead.

In all cases we will state that, in the event that clinical decisions need to be made based on antibody levels, the subjects should have a test performed by an NHS Laboratory at the relevant time. This is because antibody levels may change over time.

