16. The subject is followed up by PHE actively, with weekly symptom and activity questionnaires, and passively, with weekly database (SGSS, a microbiology database containing COVID-19 results, and other appropriate queries) searches for all evaluated subjects, allowing quantification of hospitalisation with positive SARS-CoV-2 tests, a proxy for severe disease.

Study workflow (Stage two, Community testing centre):

- 1. The subject is asked to give consent to testing a HTK.
- 2. The subject is asked to complete short questions on their current behaviour over the prior weeks.
- 3. Up to 20ml venous blood sample will be obtained by a trained on-site phlebotomist exactly as in Stage 1.
- 4. The subject does a HTK without assistance, using the packaging and training proposed for home use.
- 5. The subject may optionally be asked to read the result not of their own test, but of another person, following a randomisation procedure to which the subject is blinded. The necessity for this step is discussed in Objective 2, below.
- 6. The subject takes a photo of the result on their mobile phone (perhaps with the NHSX or another appropriate app), and/or uploads the result to the NHSX designed app, or via another appropriate tested mechanism agreed with MHRA.
- 7. The result will also be independently read by a trained professional and a second independent reviewer and/or algorithm (e.g. in-app test reader).
- 8. The subject completes an additional questionnaire, including questions on ease of use and reading of the kits, acceptability of the kits etc. In some cases, structured, semi-structured interviews may occur.
- 9. The subject is thanked, given a leaflet or email providing contact details if they have any further questions.
- 10. The blood sample is sent to PHE Sero Epidemiology Unit (SEU) Laboratory in Manchester, and/or another laboratory as necessary, and analysed for anti-SARS-CoV-2 antibodies using the HPA EIA assay, and other assays as they are developed. Other experimental assays may also be used.
- 11. The lithium heparin anticoagulated sample is sent to Oxford Immunotec Ltd and processed exactly as in Phase 1.
- 12. The HTK is repeated in the laboratory on the blood sample taken, to determine whether results are the same as from the HTK when done in the community testing centre.
- 13. The subject continues to be followed up by PHE actively, and passively, as outlined previously.

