We will also report test accuracy in comparison to locally relevant adaptations of the World Health Organisation [20th March, version 6] criteria for confirmed cases (RT-PCR positive), suspect cases (combining symptoms and exposure) and probable cases (suspect cases with inconclusive or no RT-PCR results).

Our adapted definition reflects UK screening and swabbing practice; see Appendix 2. On 5 March, the UK Government confirmed that local COVID-19 transmission was occurring. After this, it changed policy from a 'containment phase' based on active case finding and molecular screening of individuals meeting a definition based on WHO criteria to one of 'delay' in which testing was largely confined to hospitalised cases, based on limitations in testing capacity.

Our definition includes the WHO's recommended confirmed, suspect and probable cases. In addition, we are pre-specifying a category of 'symptoms but tested negative' because molecular testing may be insensitive.

Our approach will otherwise be similar to that in Analysis 1a.

Analysis 2

The key assumption of Analysis 1 (that the laboratory-based assay makes no errors) is known to be untrue. In Analysis 2, we will use the "known positive" status of up to 500 of the study participants, alongside additional data, to estimate the sensitivity and specificity of both the HTK and the laboratory-based assay.

Evaluating Detection of SARS-CoV-2 antibodies using home test kits (EDSAB-HOME study)

Protocol 30.05.2020 Version 04.03

Data from multiple sources, including the present study, will be synthesised together using a Bayesian latent class modelling / multi-parameter evidence synthesis approach.

As described on page 2, we propose additional data collection through two main routes. We will also attempt to identify as many other relevant data sources as possible. Relevant studies will be those involving the HPA assay, HPA and other assays including T-SPOT Coronavirus, HPA and the home test kit, and other assays which have been compared to HPA and the home test kit. Data from studies with each of these designs will improve estimation of the accuracy of both the HTK *and* the HPA assay. Attention will be focused on:

Other studies using two or more assays on populations with unknown prevalence. Information from studies with a wide range of different (unknown) seroprevalence values can contribute useful information about the sensitivity and specificity of the assays concerned.

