Evaluating Detection of SARS-CoV-2 antibodies using home test kits (EDSAB-HOME study)

Protocol 30.05.2020 Version 04.03

assume that the accuracy of self-read tests as assessed against expert-read tests is independent of the true antibody status.

In the first analysis, we will examine the probability of a self-read positive result among expert positive results, and the probability of ("false") self-read positive result among expert negatives, both as functions of reported exposure and illness experience, using logistic regression.

The second analysis will estimate the overall Sensitivity of the self-read HTK as Pr(self-read +ve|Expert +ve) x Sensitivity of the Expert-read POC based on the evidence synthesis results (Objective 1, Analysis 2). Similarly the overall specificity of the self-read POC will be estimated as: Pr(self-read -ve|Expert -ve) x Specificity of the Expert-read HTK based on the evidence synthesis results.

Objective 3

To assess whether home photographic recording of HTK is feasible and enhances accuracy of recording relative to user reading;

If possible, we will also compare to results from an automated pixel analysis of a photograph of the test taken by the person tested, and a visual analysis of a photograph taken under optimal conditions in the field. We will report concordance between the methods of interpreting results, and characteristics of discordant results (including whether they are positive or negative using the HPA test).

Objective 4

To determine the acceptability of the tests to the population;

Data (including both quantitative and free text) obtained from the baseline questionnaire on acceptability and usability of the HTK programme completed by participants will be summarised by counts, descriptive statistics and pseudo-anonymised quotes. In addition, work conducted by user researcher team at NHSX and qualitative interviews conducted prior and during the pilot phase of the programme will be included into the results of the evaluation, where appropriate/necessary.

Objective 5

To inform the instructions and other advice to be provided to people undertaking the tests and to those who have a positive and a negative result;

Results obtained on the sensitivity and specificity of the HTK will inform what advice should be given, including whether confirmatory testing using laboratory based tests will be necessary for any subsets of the population, including healthcare workers.

Objective 6

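### The Objective 2 product for self-read sensitivity has no term linking the participant-run kit to the laboratory-run kit, so any loss from participants performing the test is left out

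*Protocol*

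**What the plan says.** Protocol, Statistical Analysis, Objective 2 fixes the formula as a product of two factors. The first is the reading probability: "The second analysis will estimate the overall Sensitivity of the self-read HTK as Pr(self-read +ve|Expert +ve"). The second factor, by which that probability is multiplied, is given as: "x Sensitivity of the Expert-read POC based on the evidence synthesis results (Objective 1, Analysis 2"). Specificity is built the same way from negative readings.

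The two factors come from different parts of the study.

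- **Second factor.** Under Three stages, stage one: "A plasma bank will be set up, ready to be tested with the HTK in the laboratory once available". Step 14 of the stage one workflow repeats this: "Banked plasma is made available for laboratory evaluation of HTKs in a laboratory setting, when such kits become available". The stage one text names two accuracy analyses, the second being "Bayesian evidence synthesis methods incorporating other data sources (see below). (Objective 1, 6, 7"). Analysis 2 widens the inputs: "Data from multiple sources, including the present study, will be synthesised together using a Bayesian latent class modelling / multi-parameter evidence synthesis approach".
- **First factor.** Step 4 of the stage two workflow: "The subject does a HTK without assistance, using the packaging and training proposed for home use". At step 7 a trained professional reads that result independently.

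Stage two also collects data that could join the two. Step 10 gives a same-visit result on the High Performance Assay (HPA), the laboratory reference. Step 12 adds a laboratory repeat: "The HTK is repeated in the laboratory on the blood sample taken, to determine whether results are the same". The comparison is with the participant's own run of the kit at the centre. The Objective 2 formula uses neither.

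**The concern.** The word Expert stands for two different tests in one product. In the first factor the expert reads a device the participant ran. In the second, as far as this study's own Objective 1 data go, the expert reads a kit run in the laboratory. The product is valid as it stands only if a kit run by a participant is positive whenever the laboratory-run kit would be.

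The planned agreement analysis cannot reveal a failure of that condition. If a participant applies the sample or runs the kit badly and no test line appears, participant and expert both read negative, and this counts as agreement. Relabelling devices between participants deals with reading bias only, since the devices are still participant-run. Objective 3 describes HPA status for results that differ between reading methods, so a device that every reader calls negative is not picked up there either.

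The result is presented as the sensitivity of self-read tests in reflecting antibody status, and under Objective 5 accuracy results inform the advice to users and the decision on confirmatory testing.

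**Working it through.** The protocol states no numerical result for this product, so there is no figure to reproduce. The check writes out the full expression and compares it with the product.

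**Inputs**

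- Se = 0.98, the HTK sensitivity assumed under Sample Size for Analysis 1 of Objective 1.
- r = Pr(self-read positive, given expert positive) = 0.97. Assumed.
- f = Pr(self-read positive, given expert negative) = 0.01. Assumed.
- L = share of laboratory-detectable positives lost when the participant runs the kit: 0, 1%, 5%, 10%. Assumed.

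The protocol's own assumption is kept: reading accuracy relative to the expert does not depend on antibody status. It is also assumed that participants only lose positives and gain none.

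**Formulas**

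- Plan: r × Se = 0.97 × 0.98 = 0.9506.
- Expert-read sensitivity of the participant-run device: e = Se × (1 − L).
- Self-read sensitivity of the participant-run device: r × e + f × (1 − e).

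| L | e | r × e | f × (1 − e) | Sum | Plan minus sum |
|---|---|---|---|---|---|
| 0 | 0.9800 | 0.9506 | 0.0002 | 0.9508 | −0.0002 |
| 1% | 0.9702 | 0.9411 | 0.0003 | 0.9414 | 0.0092 |
| 5% | 0.9310 | 0.9031 | 0.0007 | 0.9038 | 0.0468 |
| 10% | 0.8820 | 0.8555 | 0.0012 | 0.8567 | 0.0939 |

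The plan's figure stays at 0.951 whatever L is, so the loss passes almost one for one into overstatement. At L = 5% the share of antibody-positive people missed is 1 − 0.9038 = 9.6%, against 1 − 0.9506 = 4.9% by the plan.

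**The second omission.** The product also drops f × (1 − Se), positive self-readings of expert-negative devices. This works the other way but is small: 0.01 × 0.02 = 0.0002 at L = 0. The two omissions cancel at L = f(1 − Se) / [Se(r − f)] = 0.0002 / 0.9408 = 0.02%. Above that the plan overstates.

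**Other inputs.** With f = 0.02, the sums at 1%, 5% and 10% are 0.942, 0.904 and 0.858. With Se = 0.80, r = 0.95 and f = 0.03, the plan gives 0.760 against 0.759, 0.729 and 0.692, and break-even is 0.8%.

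**Specificity.** The plan gives (1 − f) × Sp = 0.99 × 0.98 = 0.9702. The full form is (1 − f) × Sp* + (1 − r) × (1 − Sp*), where Sp* is the expert-read specificity of the participant-run device. The omitted reading term is 0.03 × 0.02 = 0.0006 if Sp* = Sp. Whether Sp* lies above or below Sp cannot be told from the protocol.

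**The case against.** Several points on the other side have force.

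- **The second factor is not purely laboratory data.** Analysis 2 takes outside studies and does not exclude stage two data. Stages one and two may be combined, and whether and on what scale Objective 1 is done is left to the Department of Health and Social Care with the regulator. This stands: a reader might infer that the second factor comes only from laboratory-run plasma, and the protocol does not fix that. But mixing sources does not make the two expert readings the same test, and no term is defined to join them.
- **The transfer is checked.** Step 12 compares the laboratory repeat with the testing-centre result, and the stage two description includes laboratory reading among the agreements assessed. This stands in part: the data are collected. But the formula does not use them, and Objective 2 gives no rule for the case where they disagree. A formula fixed in the protocol is not detail left to an analysis plan.
- **The size is assumed, and predictive value moves little.** Both are true. The protocol calls positive predictive value the metric of most interest. With specificity held at 0.98, a fall in sensitivity from 0.951 to 0.904 takes it from 0.841 to 0.834 at 10% prevalence and from 0.922 to 0.919 at 20%. The effect falls on missed positives. Runs that give an invalid result are also not necessarily missed positives.
- **Estimating against the HPA alone would treat it as error-free**, which Analysis 2 is meant to avoid. This stands and shapes the fix.

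A reader might also infer a capillary-versus-plasma difference, or a bias in sensitivity at home. The protocol does not call the HTK a finger-prick test; its roughly 100 capillary samples serve immunoassay optimisation. Stage two takes place at a testing centre, so neither inference is supported. Unassisted participant use is explicit, and that is enough for the point.

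**Conclusion.** The point holds as a structural gap in a stated formula. The product joins a reading probability on participant-run devices to a sensitivity that, for this study's own Objective 1 data, describes laboratory-run kits, and nothing links the two. Sensitivity will be overstated to the extent that participants lose positives the laboratory kit would detect. On the assumptions above, this is about 0.9, 4.7 and 9.4 percentage points at losses of 1%, 5% and 10%.

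The protocol does not establish that such loss occurs, or how large it is. An unconditional statement that sensitivity is overstated would therefore go too far. For specificity the gap is the same and the direction open.

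**What to change.** Preferred: enter the stage two self-read, photo-read and community expert-read results as additional tests in the Analysis 2 latent-class model, together with the same-visit HPA result (step 10) and the laboratory HTK repeat (step 12). Allow for stage two sampling, which may depend on EIA result and symptom history. This yields accuracy of the participant-run kit at the testing centre without treating the HPA as perfect.

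Alternative: keep the product but add the probability of the community expert result given the laboratory HTK result, from step 12, and the omitted term for positive self-readings of expert-negative devices. Make the matching changes for specificity. Say whether the link is estimated within antibody-status groups or assumed the same across them.

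In either case, state which expert-read HTK data feed the second factor, and do not report the current product as the overall accuracy of the user-run test.

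The cost is a change to the analysis text; all the data are already planned. Intervals will be wider, because only participants who attend stage two contribute to the linking step.

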Evaluating Detection of SARS-CoV-2 antibodies using home test kits (EDSAB-HOME study)

Protocol 30.05.2020 Version 04.03

Study workflow (Stage one, Community testing centre):

- 1. The study will be advertised in target workplaces, through senior leadership at the workplace.
- 2. Patient information leaflets are distributed to interested persons, who are invited to a clinic.
- 3. Informed consent is obtained. The subject is given the option to receive results from validated assays, if these are available.
- 4. The subject completes a questionnaire, including information on their demographics, and questions (such as prior symptoms, prior symptoms in family, health care worker/school contact, and area of residence) relevant to the risk they have been exposed/infected by COVID-19. Additional questions on their current behaviour will also be included.
- 5. Up to 20ml venous blood sample will be obtained by a trained on-site phlebotomist. We will take 1x 6ml EDTA anticoagulated samples and 1 x 6ml or 10ml lithium heparin anticoagulated tube. This may occur in a specially convened clinic; alternatively, if before the visit, the NHS decided to start staff antibody screening, we will do our best to coordinate and make sure that any blood samples needed are all taken in one sitting.
- 6. In a proportion of subjects, the subject may also be asked to provide a capillary blood sample and/or dried blood spot. They will be assisted in doing so.
- 7. The subject is asked whether they would like to be a volunteer who may be called back for further testing.
- 8. The subject is thanked, given a leaflet or email explaining that we may contact them again to take part in stage two, and what that would involve.
- 9. The EDTA venous blood sample is sent to a PHE Sero Epidemiology Unit (SEU) Laboratory in Manchester, and/or another laboratory as necessary. Plasma will be separated by centrifugation.
- 10. If the subject has specifically consented, waste material not used for serological analysis (including blood cells and DNA) is banked for future studies. Recent experiments have shown the immune response can be analysed by analysing the DNA rearranged during T cell and B cell receptor formation (see: Fowler A et al 2020 BMC Genomics 20202 21:176). Such studies may be the basis of prognostic tests in the future, so banking this is relevant to the COVID-19 containment campaign.
- 11. Plasma is banked.

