As above, in the event that antibody kits are available earlier than expected, and at scale, stage one and two may be combined with all subjects in stage one (above) additionally using HTKs (steps 4-7 of Stage 2) after step 4 of stage one.

Evaluating Detection of SARS-CoV-2 antibodies using home test kits (EDSAB-HOME study)

Protocol 30.05.2020 Version 04.03

Study workflow (Stage three, Extension to home setting):

- 1. The subject is identified through the NHSX HTK service and is asked to give consent for participation
- The subject is sent a questionnaire to complete, including information on their demographics, questions relevant to the risk of infection by COVID-19, and questions on their current behaviour. We anticipate this will either be an online system, e.g. SelectSurvey or Snap Survey, or integrated directly into the NHSX app.
- 3. The subject is asked to complete their HTK, following the instructions provided to them.
- 4. The subject records their result and photographs their kit in the NHSX system, or another tested alternative system.
- 5. The subject completes further questions around the acceptability and usability of the kits, including specific questions around the ordering of the kit through the online system.
- 6. The subject is thanked for their participation.
- 7. The subject is followed up by PHE actively, with weekly symptom and activity questionnaires, and passively, with weekly database (SGSS, a microbiology database containing COVID-19 results, and other appropriate queries) searches for all evaluated subjects, allowing quantification of hospitalisation with positive coronavirus tests, a proxy for severe disease.

Follow-Up:

Some participants from stage one may be invited back to participate in stage two. Participants will be actively followed up through weekly questionnaires, and passively followed up through data linkage with routine databases.

Evaluating Detection of SARS-CoV-2 antibodies using home test kits (EDSAB-HOME study)

Protocol 30.05.2020 Version 04.03

Figure 2: Flow diagram of the three-stage evaluation study methodology

Evaluating Detection of SARS-CoV-2 antibodies using home test kits (EDSAB-HOME study)

Protocol 30.05.2020 Version 04.03

Data management and analysis

Data Management and Quality Assurance

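### If stages one and two are combined, the workflow as written omits the post-use questionnaire on usability and acceptability, and the Objective 4 analysis names a baseline questionnaire as its source

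*Protocol*

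**What the plan says.** Under Statistical Analysis, Objective 4, the protocol says that acceptability and usability will be summarised by counts, descriptive statistics and quotes, from data "obtained from the baseline questionnaire on acceptability and usability of the HTK programme completed by participants". It adds work by the NHSX user research team, and says that "qualitative interviews conducted prior and during the pilot phase of the programme will be included into the results of the evaluation", where appropriate or necessary.

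The workflows describe these questionnaires around kit use:

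- **Stage one, step 4 (entry).** "The subject completes a questionnaire, including information on their demographics, and questions" on the risk of exposure or infection, with further questions on current behaviour. Under Three stages, the stage one participants "are recruited (2,500 persons) prior to the HTKs becoming available".
- **Stage two, step 8 (after the kit is done, photographed and read).** "The subject completes an additional questionnaire, including questions on ease of use and reading of the kits, acceptability of the kits etc". Interviews may follow in some cases.
- **Stage three, step 2 (before the kit).** Demographics, infection risk and behaviour.
- **Stage three, step 5 (after the kit).** Further questions on acceptability and usability, including ordering the kit online.

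The paragraph after the stage two workflow gives a contingency: "in the event that antibody kits are available earlier than expected, and at scale, stage one and two may be combined", with all stage one subjects "additionally using HTKs (steps 4-7 of Stage 2) after step 4 of stage one". The same contingency is also described under Three stages.

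**The concern.** Ease of use and ease of reading a kit can be reported only by someone who has used it. The combined route brings the kit into stage one but, read literally, leaves behind the form that asks about using it. Impressions not collected at the visit cannot be recovered later by an analysis plan, so this is a matter of study conduct for the protocol to settle.

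The word baseline in the Objective 4 analysis adds to the difficulty. It directs the reader to an entry form, whereas the workflows place the relevant items after kit use. Someone who relied on that sentence when setting up the combined route would have no prompt to notice that step 8 had dropped out.

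At stake are Objective 4 and Expected outcome 4, which promises questionnaire responses on the acceptability and usability of the kits.

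**Working it through.** No figure in the protocol is at issue. The check is a comparison of workflow steps.

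**1. What the combined route carries over.** Stage two has 13 steps. The clause imports steps 4 to 7, which is 4 steps: doing the kit, optionally reading another person's result, photographing it, and independent reading. That leaves 13 − 4 = 9 steps not imported.

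**2. Whether stage one already covers those 9 steps.**

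| Stage two step not imported | Stage one counterpart |
|---|---|
| 1 Consent | Step 3 |
| 2 Behaviour questions | Step 4 |
| 3 Venous blood | Step 5 |
| 8 Post-use questionnaire | None |
| 9 Thanks and leaflet | Step 8 |
| 10 Laboratory antibody assay | Step 13 |
| 11 T-SPOT | Step 12 |
| 12 Laboratory HTK | Step 14 (banked plasma made available for it) |
| 13 Follow-up | Step 16 |

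Eight of the nine have a counterpart, although not always an exact one. Only step 8 has none. The weekly questionnaires in stage one step 16 cover symptoms and activity, not the kit.

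**3. Order within the combined route.** The kit steps are inserted after stage one step 4. The entry questionnaire is therefore completed before the kit is handled on this route too, and cannot serve as the post-use form.

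**4. Size.** Under Three stages, the combined option applies to all stage one subjects, planned at 2,500. The number scheduled for a structured post-use questionnaire at the testing centre on that route, as written, is 0.

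**5. The named data source.** The protocol does not define the baseline questionnaire. The two forms given before the kit (stage one step 4, stage three step 2) list no acceptability or usability items; the two given after it (stage two step 8, stage three step 5) do. The label and the workflows do not match.

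**6. Whether cross-references resolve it.** Under Three stages, stage two is tagged to Objectives 2, 3, 5 and 6, and stage three to Objective 5. The only text there tagged to Objective 4 is the weekly symptom follow-up and record linkage, which concern disease progression. The analysis section also restates Objective 4 without the word usability, which the objectives list includes. No tag links the post-use questionnaires to Objective 4.

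**The case against.** **The range of steps may be shorthand.** It can be read as saying where kit handling is inserted, not as a full list of what is kept; it also leaves out consent and the laboratory repeat of the kit, and nobody would take those as cancelled. This is fair, and nothing in the protocol says that step 8 is cancelled. But the other omitted steps have stage one counterparts and step 8 does not, so a site following the text would have no instruction to give that form.

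**Baseline may be a loose word.** The sentence identifies the form by its content, and an analyst would look for the form that holds those items. The lists of entry questions are also introduced as examples and are not closed. This largely stands: the risk of analysing the wrong form is small, and that half of the point is a mislabelled source.

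**Acceptability of a programme can be asked before use.** True, but no such item is listed in either entry form, and the argument does not extend to ease of use and reading.

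**A reader might infer that usability would have no valid measurement at all.** The protocol does not support that. The standard stage two and stage three both ask about the kit after use, stage three is expressly directed at usability, and user research and interviews are further sources. The combined route is also conditional on kits arriving early and at scale.

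**Conclusion.** The point holds in a limited form. If the combined route is used as written, Objective 4 would have no structured post-use questionnaire data from the testing centre, for any of the 2,500 planned stage one participants. The stage three questions would remain, but they come from people identified through the NHSX service who use the kit at home, so they would complement the testing-centre data without replacing them. Separately, the Objective 4 analysis names a source that does not match the workflows.

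This rests on two readings: that the step range is meant literally, and that the baseline questionnaire means a form given at entry. The first follows from the text; the second is inferred, since the term is undefined.

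Severity is minor to moderate. Objective 4 is descriptive, no accuracy estimate or sample size depends on it, and the standard route already collects the data after use. It still merits correction, because the first part changes what would be collected and an omission at the visit could not be made good afterwards.

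**What to change.** Two edits:

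1. In the combined-stage paragraph after the stage two workflow, extend the imported range from stage two steps 4-7 to steps 4-8, so that the post-use questionnaire follows the kit.
2. Under Statistical Analysis, Objective 4, replace the reference to the baseline questionnaire with the questionnaires completed after kit use: stage two step 8 and stage three step 5.

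While editing, it would help to restore usability to the Objective 4 wording in the analysis section and to tag stages two and three to Objective 4 under Three stages.

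The questionnaire is already planned for stage two, so no new instrument is needed. The cost is an estimated few minutes per participant, on the combined route only; the standard route is unchanged.
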